3.2 Secondary Objectives

The following secondary objectives will be used to support the results of the primary objective:

1. Assess independent effects of three active concentrations of marijuana and placebo in reducing self-reported symptoms of PTSD with the PCL-5, anxiety and depression with the IDAS, and improving psychosocial functioning with the IPF and WBR (self-report and observer) among veterans during Stage 1.
2. Assess independent effects of three active concentrations of marijuana and placebo in reducing self-reported symptoms of PTSD with PCL-5, anxiety and depression with IDAS, and improving psychosocial functioning with the IPF and WBR (self-report and observer) among veterans during Stage 2.
3. Assess comparative efficacy between placebo and each active dose of marijuana based on a within-subjects analysis of PTSD symptoms as measured by the CAPS-5 in crossover participants at Baseline, End of Stage 1, Stage 2 Baseline, and End of Stage 2.
4. Assess whether Stage 2 crossover participants' preferences for marijuana concentrations in Stage 1 and Stage 2 correlate with reduction in PTSD symptoms as measured by the CAPS-5 total score.
5. Assess whether participants experience a clinically significant increase in PTSD symptoms based on CAPS-5 and PCL-5 total scores during the washout period between Stage 1 and Stage 2 compared with measures assessed at Baseline and during Stage 1.
6. Explore correlation of treatment outcomes measured by CAPS-5 score with objective changes in sleep via Actigraphy throughout the study and self-reported

- changes in sleep quality using the ISI on a weekly basis.
7. Explore correlation of Daily Diary items related to sleep with objective changes in sleep via Actigraphy and self-reported changes in sleep quality using the ISI on a weekly basis.
 8. Explore correlation of treatment effects measured by CAPS-5 total score with amount of marijuana used based on Daily Diary across Stage 1 and Stage 2.
 9. Explore treatment outcomes measured by CAPS-5 total score by marijuana concentration, with concomitant substance and medication use as a covariate throughout the treatment period.
 10. Explore durability of treatment outcomes measured by CAPS-5 total score, with any PTSD treatments based on the LTFU questionnaire treated as a covariate, six months after completing Stage 2.

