4.0 Protocol Design

This Phase 2 randomized, placebo-controlled, triple-blind, crossover, multi-site study will assess the safety and efficacy of four types of smoked marijuana to manage chronic, treatment-resistant PTSD symptoms among 76 veterans in an outpatient setting. The study will consist of a baseline period and three distinct study stages, which are described in detail below.

An initial 2-week screening period will be conducted to determine study eligibility prior to randomization, to obtain baseline measures of PTSD and substance use, to conduct study training, and ensure participants are willing and able to attend scheduled appointments and complete the study procedures.

Following randomization, participants will complete Stage 1, a three-week period of *ad-libitum* marijuana self-administration followed by a two-week period of marijuana abstinence (Cessation 1). This will be immediately followed by Stage 2, another three-week period of marijuana self-administration and two-week period of abstinence (Cessation 2). Stage 1 and Stage 2 will consist of identical procedures and measures, but the marijuana available to individual participants will vary.

During Stage 1, participants will be randomized to receive High THC, High CBD, THC/CBD, or Placebo marijuana to self-administer (up to 1.8 g/day) for the 3-week marijuana use period. As described in Section 4.2, randomization will be balanced across drug conditions (N=19 per marijuana type; total N=76). During Stage 2, the Placebo marijuana condition will be removed and all participants will be re-randomized to receive a different type of marijuana than they were assigned in Stage 1. Thus, Stage 2 will permit a within-subjects comparison of changes in CAPS-5 total score as a function of marijuana concentration, including differences in preferences for a specific marijuana concentration by self-report, and the removal of placebo as a possibility ensures that all study participants receive active marijuana at some point during the study.

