12.0 Data Analysis

Key Personnel, MAPS, and the biostatistician will agree on a detailed Statistical Analysis Plan prior to the beginning of recruitment. The biostatistician will perform an "intent to treat" (ITT) analysis using repeated measures analysis of covariance (ANCOVA) to compare demographics. Distribution of treatment dropouts will be examined by condition and if found to be unequal, the sponsor will control for group assignment in the ITT analysis.

Primary analysis of observer-blind CAPS-5 data collected at Baseline and end of Stage 1 will be conducted using ANCOVA with marijuana concentration as a between-subject factor and time of assessment as a within-group factor. If effects of marijuana concentration are detected at Stage 1, a similar secondary analysis will also be performed with Stage 2 data using Stage 1 data as a covariate for each outcome measure. Effect size will be estimated based on all outcome measures using Cohen's techniques. The biostatistician will conduct secondary exploratory analyses of weekly assessments of PCL-5, ISI, IDAS, IPF, WBR, CSSRS, MWC, CUDIT-R, DEQ and ACT scores using repeated measures ANCOVA or generalized linear mixed modeling, as described in the Statistical Analysis Plan. Statistical significance ($p < .05$) will be determined for all tests. All available data from repeated outcome assessments of all participants who are randomized, even if they withdraw from the allocated treatment prior to the primary endpoints, will be included in ITT analysis.

A repeated measures ANCOVA comparison of ratings on the DEQ and pulse will be conducted, with marijuana condition as the main factor in the analysis. If a main effect of marijuana concentration is observed then pairwise comparisons will be conducted to detect differences between each marijuana concentration.

Secondary exploratory analyses will be conducted examining weekly assessments of self-reported (via the ISI) and objective (via Actigraphy) measures of sleep. Independent repeated measures ANCOVAs will be conducted. In terms of self-reported sleep, weekly total scores from the ISI will be entered as the repeated measure with group entered as the IV. In terms of objective sleep (via Actigraphy) repeated measures ANCOVAs will be conducted with weekly total sleep time (TST), wake after sleep onset (WASO), sleep

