onset latency (SOL), and sleep efficiency (SE) entered as the repeated measure in independent analyses and group entered as the IV. An ITT approach will be used. Statistical significance will be set at $p = .05$ for all analyses.

Quantitative levels of THC, CBD and their metabolites will be assessed in order to ascertain whether participants comply with only using the marijuana assigned to them during the study. If there is sufficient data, correlational analyses may also be conducted between biological cannabinoid levels and clinical outcomes to determine whether there is a dose-response effect between cannabinoid exposure and clinical response.

Prognostic value of CRP, IL-1 β and Il-6 will be examined using two regression analyses, one between biomarker values gathered at Baseline and at the primary endpoint CAPS-5 global severity score, and another between biomarker values collected after two weeks of cessation and the CAPS-5 global severity score at the end of Stage 1.

Qualitative safety analyses will examine Daily Diaries with summary tables listing maximum severity and duration, concomitant medications/therapies, and AEs with frequencies and percentages tabulated overall and by concentration group. Spontaneously reported reactions will be separated from unexpected AEs during analysis and presented separately in summary tables. Statistical analyses will be conducted to evaluate safety and AEs by marijuana treatment condition and individual demographic characteristics (e.g. gender, history of cannabis use, concomitant medication/drug use, baseline CAPS-5 score).

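### The crossover is there for a within-participant CAPS-5 comparison of products, but the CAPS-5 Stage 2 analysis named in 12.0 compares groups and cannot answer Secondary Objective 3

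*Protocol*

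**What the plan says.** Protocol 4.0 gives the purpose of the second stage: "Stage 2 will permit a within-subjects comparison of changes in CAPS-5 total score as a function of marijuana concentration". Secondary Objective 3 in 3.2 is more specific: "Assess comparative efficacy between placebo and each active dose of marijuana based on a within-subjects analysis of PTSD symptoms". It applies to crossover participants and names four CAPS-5 time points: Baseline, End of Stage 1, Stage 2 Baseline and End of Stage 2.

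Section 12.0 describes the primary Stage 1 analysis as "ANCOVA with marijuana concentration as a between-subject factor and time of assessment as a within-group factor". The Stage 2 CAPS-5 analysis follows from it, under a condition: "If effects of marijuana concentration are detected at Stage 1", then "a similar secondary analysis will also be performed with Stage 2 data using Stage 1 data as a covariate for each outcome measure". Section 12.0 also plans exploratory analyses of weekly measures "using repeated measures ANCOVA or generalized linear mixed modeling, as described in the Statistical Analysis Plan"; CAPS-5 is not in that list.

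Under 4.0 and 4.2, nobody receives placebo in Stage 2 or repeats their Stage 1 product.

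**The concern.** Each participant who continues is rated on two products. A model for that design compares a person's response on one product with the same person's response on the other. The analysis named in 12.0 treats Stage 2 as a second parallel-group trial: product varies only between people, and the Stage 1 result enters as an adjustment variable although it is itself a response to one of the products under study.

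Two things are at stake. The first is Objective 3: a Stage 2 group comparison contains no placebo group, so it yields no placebo contrast of any kind. The second is precision on whether the THC:CBD ratio matters, which 2.1 and 2.3 give as a purpose of the study. That is an active-versus-active question, and participants undergo a second three-week exposure and a second cessation partly to inform it.

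**Working it through.** **The plan's own figure.** Section 12.1 states 82% power for N = 76 in four groups of 19 with effect size 0.4. Read as Cohen's f in a one-way F test, the noncentrality is 76 × 0.4² = 12.16 on 3 and 72 df, which gives 82.3%, so the figure reproduces. It describes the overall Stage 1 test. No figure is given for a Stage 2 or pairwise contrast, although 12.1 extends the reasoning to secondary analyses.

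**Inputs.**
- From the documents: 19 per Stage 1 arm (4.0), 1:1 re-randomization to two new products (4.2), level 0.05 (12.0).
- Stage 2 numbers: Table 4 sends placebo participants to High THC or High CBD, giving 28.5 / 28.5 / 19 for High THC / High CBD / THC/CBD (9.5 per sequence). Table 6 (25 / 25 / 26) fits three destinations, about 25.3 each. Both are run.
- Assumed: two-sided tests, unit SD, no Stage 2 dropout, no carryover, between-stage CAPS-5 correlation ρ of 0.3-0.7, and a benchmark pairwise difference of 0.4 SD. This 0.4 is not the f of 12.1.

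**Formulas.** For products a and b:
- Stage 2 ANCOVA variance = (1 − ρ²)(1/n_a + 1/n_b).
- Stage 1 variance = 2/19 = 0.1053 (SE 0.324).
- Both-stage variance: generalized least squares with terms for mean, stage and current product, and within-person covariance [[1, ρ], [ρ, 1]].
- Power: noncentral t, 70 df.

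Worked case, High THC versus THC/CBD, Table 4, ρ = 0.5: 0.75 × (1/28.5 + 1/19) = 0.0658, SE 0.256. The both-stage variance is 0.0294, SE 0.171. Share kept: 0.0294 / 0.0658 = 45%.

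| Contrast, allocation | ρ | Stage 2 ANCOVA variance | Both-stage variance | Share kept | Power at 0.4 SD |
|---|---|---|---|---|---|
| High THC vs THC/CBD, Table 4 | 0.3 | 0.0798 | 0.0383 | 48% | 29% vs 52% |
| | 0.5 | 0.0658 | 0.0294 | 45% | 34% vs 63% |
| | 0.7 | 0.0447 | 0.0188 | 42% | 46% vs 82% |
| High THC vs High CBD, Table 4 | 0.3 | 0.0639 | 0.0342 | 54% | 35% vs 57% |
| | 0.5 | 0.0526 | 0.0263 | 50% | 41% vs 68% |
| | 0.7 | 0.0358 | 0.0168 | 47% | 55% vs 86% |
| Any active pair, three destinations | 0.5 | 0.0592 | 0.0279 | 47% | 37% vs 66% |

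Stage 1 alone has 23% power for any of these pairs.

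**Stage 1 product left out.** Adjusting for the Stage 1 score without the Stage 1 product distorts a true difference, because people on product a in Stage 2 cannot have had a in Stage 1. With three destinations, 9.5/25.33 = 0.375 of those on a came from b, and the reverse. The groups therefore differ by −0.375 × 0.4 = −0.15 SD on the covariate, and the adjusted estimate is about 0.4 + 0.15ρ, that is 0.44-0.51 for ρ of 0.3-0.7. There is no distortion under the null. Adding Stage 1 product removes it, but for High THC versus THC/CBD (Table 4, ρ = 0.5) it raises the SE to 0.308 and lowers power to 25%.

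**Placebo contrasts.** The Stage 2 analysis contributes nothing. At ρ = 0.5 the both-stage variance for High THC or High CBD versus placebo is 0.0598 (Table 4) or 0.0619 (three destinations). Stage 1 alone thus holds 0.0598/0.1053 = 57% or 0.0619/0.1053 = 59%. For THC/CBD versus placebo under Table 4 the share is 0.0685/0.1053 = 65%. Placebo always comes first, so a simple paired comparison in placebo-first participants would confuse product with stage. The stage term, estimated from the active-to-active sequences, separates them.

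**The case against.** Much of the case on the other side stands.

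- **A reader might infer that most of the product information goes unused.** The documents do not support that. The Stage 1 covariate already uses the within-person correlation, and the primary analysis already uses Stage 1. Adding the information of the two stated analyses (at ρ = 0.5, 45% + 28% = 73% for High THC versus THC/CBD), 60-86% is kept over ρ of 0.3-0.7 for the two Table 4 pairs. But 12.0 names no way to combine them, so neither reported interval has that precision.
- **A reader might infer that this is the only Stage 2 analysis.** It is not: the weekly exploratory models are not limited to Stage 1. It is the only CAPS-5 Stage 2 product analysis named.
- **A reader might infer that the within-person contrast will never be estimated.** Objective 3 commits to it, and the SAP, not seen here, may supply a model. However, 12.0 itself fixes the factor, the data and the covariate for Stage 2 CAPS-5 and refers to the SAP for method only for the weekly measures. That is a stated method that does not fit the objective, not simply detail left for later.
- **Pooling has a price.** It assumes limited carryover after two weeks and similar product effects in both stages, although expectancy may change once placebo is removed. Comparing the stage-specific estimates is a weak check: treated as independent, their difference has SE √(0.1053 + 0.0658) = 0.41, so only a discrepancy near 2.80 × 0.41 = 1.15 SD is detectable with 80% power.
- **The figures are idealised.** With 66% Stage 2 retention (an assumption), both-stage power falls from 63% to 52%; the Stage 2-only SE also grows, to 0.256/√0.66 = 0.32. The calculation leaves out the baseline covariate.

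**Conclusion.** The mismatch is real and lies in the protocol's own text: a within-participant objective is paired with a between-group analysis. The Stage 2 CAPS-5 analysis cannot deliver Objective 3, because it has no placebo group. For active-versus-active contrasts it keeps about half (42-54%) of the both-stage information, which at ρ = 0.5 and 0.4 SD means 34% against 63% power for High THC versus THC/CBD. These sizes rest on an assumed correlation, 19 per Stage 1 arm, no Stage 2 dropout and no carryover. They also assume that the Stage 2 analysis is run; whether it should depend on a Stage 1 effect is a separate question. The both-stage model would not make this pilot well powered for placebo contrasts: at 0.4 SD and ρ = 0.5, power for High THC versus placebo rises only from 23% to about 36%. The primary Stage 1 test is not affected.

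**What to change.** In 12.0, name as the secondary analysis for Objective 3 and for product contrasts a mixed model on the end-of-Stage-1 and end-of-Stage-2 CAPS-5 totals (Visits 5 and 12). Include baseline CAPS-5, current product, stage and a participant random effect. Report active-versus-placebo and active-versus-active contrasts with confidence intervals. These two visits use the same last-month rating (5.2.9), whereas the Stage 2 Baseline rating covers the last week (5.2.11); since Objective 3 lists that time point too, say how it will be used.

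Keep the Stage 1 between-group test as primary. Report the Stage 2-only comparison as a sensitivity analysis, and state the carryover and equal-effect assumptions along with the limited ability to check them.

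The cost is a change of wording and one more model. No new visits, data or participants are needed.

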Another potential mechanism by which marijuana may confer benefit in the treatment of PTSD relates to reductions in inflammation. A longitudinal study in US Marines reported an association between higher pre-deployment levels of C-reactive protein (CRP) and post-deployment development of PTSD [70]. In other research, reduction in PTSD symptoms following treatment with SSRIs was associated with a reduction in interleukin-1Beta (IL-1 β) [71], and women whose PTSD symptoms were in remission exhibited lower levels of CRP and interleukin-6 (IL-6) compared with those with current PTSD [72]. Further, a meta-analysis supported a link between IL-1 β and IL-6 and exposure to trauma [73], with stress-related elevation in IL-6 potentially higher among those with PTSD [72, 74]. Because both THC and CBD have potent anti-inflammatory and immunomodulatory properties [75, 76], marijuana use may have therapeutic benefit in PTSD treatment simply via reductions in inflammation. Biomarkers of inflammation will be assessed to investigate whether the anti-inflammatory properties of THC/CBD mediates the treatment effect of marijuana on PTSD symptom expression.

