3.4 Process Objectives

The following objectives will include exploratory analyses intended to inform future studies:

1. Evaluate protocol compliance based on comparison of Daily Diary entries, including information on amount, time and frequency of marijuana use, and the weight of any unused marijuana across each study stage.
2. Evaluate protocol compliance using quantitative blood and/or urine cannabinoid levels.
3. Evaluate whether markers of inflammation CRP, IL-1 β , and IL-6 levels in blood predict PTSD severity at baseline and treatment outcome as a function of marijuana concentration.
4. Assess the ability of site staff and participants to accurately guess condition assignment in Stage 1 and Stage 2.

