5.0 Methods

5.1 Assessments and Measures

5.1.1 Outcome Measures

Primary Outcome Measure:

The Clinician-Administered PTSD Scale (CAPS-5) [78] is a semi-structured clinical interview administered by a blinded IR and is used to assess index history of DSM-5-defined traumatic event exposure [79], including the most distressing event, time since exposure, and total number of exposures, as well as frequency and severity of posttraumatic stress symptoms, as evidenced by CAPS-5 total score. The CAPS-5 provides diagnostic status (presence versus absence) of PTSD as well as PTSD symptom severity. Changes in the CAPS-5 total score will be used as the primary PTSD outcome measure, and will be the primary determinant of effect size for this pilot study. The IR will administer the CAPS at visits described in the Time and Events table either in person or via telemedicine. IRs will receive training on administering this measure from a research reliable trainer. Interviews will be recorded in as many instances as necessary to establish reliability of a random selection of interviews for accuracy. The CAPS-5 will be

administered by trained interviewers throughout the study, who will be supervised by qualified personnel.

Secondary Outcome Measures:

The PTSD Checklist (PCL-5) with LEC plus criterion A (at baseline only) [80] is a 20-item self-report questionnaire in which respondents indicate the presence and severity of PTSD symptoms, derived from the DSM-five symptoms of PTSD [79]. Participants indicate how much distress they have experienced due to symptoms such as “Repeated, disturbing memories, thoughts, or images of a stressful experience from the past,” “Trouble remembering important parts of a stressful experience from the past,” and “Feeling irritable or having angry outbursts” on a five-point Likert-type scale (1=*not at all*, 5=*extremely*). The total PCL-5 score (a sum of all 20 items) provides an index of overall PTSD symptom severity.

The Inventory of Depression and Anxiety (IDAS) [81] is a 64-item self-report measure of depression and anxiety symptoms. Factor analytic research indicates that the IDAS has strong convergent and discriminate validity, as well as criterion validity [82]. Additionally, factor analytic research indicates that the general depression and anxiety subscales of the IDAS differentiate anxiety from depression [81, 82].

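### Neither biomarker regression in Section 12.0 uses baseline CAPS-5, so a marker that only tracks starting severity can be reported as predicting treatment outcome

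*Protocol*

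**What the plan says.** Section 3.4, item 3, sets out to learn whether CRP, IL-1beta and IL-6 "levels in blood predict PTSD severity at baseline and treatment outcome as a function of marijuana concentration". The section introduces its objectives with "The following objectives will include exploratory analyses intended to inform future studies".

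Section 12.0 gives the analysis in a single sentence that fixes two regressions. It words the first as "one between biomarker values gathered at Baseline and at the primary endpoint CAPS-5 global severity score". The second takes its markers from a later blood draw and is worded as "another between biomarker values collected after two weeks of cessation and the CAPS-5 global severity score at the end of Stage 1". No covariate is named for either.

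Three other places bear on this:

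- Section 5.1.1 defines outcome as a change: "Changes in the CAPS-5 total score will be used as the primary PTSD outcome measure".
- Section 12.0 does name adjustment elsewhere. The Stage 2 analysis is done "using Stage 1 data as a covariate for each outcome measure", and baseline CAPS-5 is listed among the characteristics for the safety analyses.
- Section 2.2.2 gives the background for a link between the markers and PTSD status: "women whose PTSD symptoms were in remission exhibited lower levels of CRP and interleukin-6 (IL-6) compared with those with current PTSD".

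**The concern.** Objective 3 holds two questions: does the marker go with severity at baseline, and does it predict how the participant fares on treatment? Neither stated regression has baseline CAPS-5 as its response, so the first question has no stated analysis. Neither has it as a covariate, so the second is mixed with the first.

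The same scale is given to the same people at Screen 2 and after three weeks of self-administration, so some correlation between the two scores is to be expected. If a marker is also related to the Screen 2 score, it will correlate with the later score through that route alone. Called prognostic, it would be read as a predictor of treatment outcome. The objective exists to inform later studies, and a marker mislabelled in this way could misdirect them.

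**Working it through.** **Plan's own figure.** The protocol states none for these regressions. The 82% in Section 12.1 concerns the comparison of the four groups. It reproduces as a four-group F test with Cohen's f = 0.4 and N = 76 (82.3%) but has no bearing here, apart from supplying N.

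**Inputs.** N = 76 (Section 12.1). Significance level 0.05 (Section 12.0), taken as two-sided. Two correlations are assumed, because the protocol gives neither:

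- a = correlation of the marker with baseline CAPS-5
- b = correlation of baseline with end-of-Stage-1 CAPS-5

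**Null case.** The marker has no relation to the endpoint once baseline CAPS-5 is held fixed. The marker-endpoint correlation is then a × b.

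**Test as written.** t = r√[(N − 2)/(1 − r²)] on 74 degrees of freedom. The critical value 1.993 corresponds to |r| > 1.993/√(1.993² + 74) = 0.226.

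**Check by hand (Fisher z), a = 0.3, b = 0.5.**

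- True correlation: 0.3 × 0.5 = 0.15, and atanh(0.15) = 0.151.
- Threshold: atanh(0.226) = 0.230. Standard error: 1/√73 = 0.117.
- Upper tail: P[Z > (0.230 − 0.151)/0.117 = 0.67] ≈ 0.25. The lower tail is under 0.001.
- Rejection is about 25%.

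**Simulation** (at least 20,000 trials per cell, trivariate normal). Chance that a marker with nothing to add beyond baseline severity is significant:

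| a | b = 0.3 | b = 0.5 | b = 0.7 | baseline CAPS-5 in model |
|---|---|---|---|---|
| 0 | 5% | 5% | 5% | 5% |
| 0.1 | 6% | 7% | 9% | 5% |
| 0.2 | 8% | 13% | 23% | 5% |
| 0.3 | 12% | 25% | 45% | 5% |

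With three markers, independent given baseline severity, and b = 0.5, the chance that at least one is significant is 35% at a = 0.2 and 57% at a = 0.3. With baseline CAPS-5 included it is about 14%, which is multiplicity alone: 1 − 0.95³ = 0.143.

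**Would a change score do?** No. In the same null case, regressing the change in CAPS-5 on the marker rejects 17-25% of the time at a = 0.3 (b from 0.7 down to 0.5), because the change is itself correlated with baseline.

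**The garbled sentence.** It may mean baseline markers against the endpoint score, or markers drawn at both Baseline and the primary endpoint against that score. Section 5.2.10 does schedule a biomarker draw at Visit 6, on the day of the primary endpoint or within two days of it. Neither reading brings in baseline CAPS-5. The figures above apply to the baseline markers under the first reading.

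**The case against.** **The text is silent about covariates and does not exclude them.** Section 12.0 promises a detailed SAP, which was not available here and may add the term. This stands in part. But the protocol has already fixed the number of regressions, the predictors and the response, and that response is the end score although Section 5.1.1 defines outcome as change. If the SAP adds the term, Section 12.0 should be aligned with it.

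**The unadjusted regression is a valid analysis.** It tests whether the marker is associated with the later score, and a marker linked to that score through baseline severity does carry some prognostic information. This stands. A reader might infer that the regression tests severity instead of prediction, or that prognostic value would be declared where none exists. Neither follows: the slope mixes the two, and at a = 0.3 with b = 0.5 to 0.7 there is a real marker-endpoint correlation of 0.15 to 0.21. The percentages are false positives only for prediction beyond baseline severity.

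**The larger correlations are unsupported.** Section 2.2.2 compares women in remission with those with current PTSD, which is a difference in status and not a gradient of severity. Everyone enrolled here has current PTSD with CAPS-5 of at least 25 (Section 4.3.1), which may weaken both correlations. This stands, and it is why the range is shown down to zero.

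**Adjustment does not always help power.** A reader might expect a general gain. For a marker with a true standardized slope of 0.25 and no correlation with baseline CAPS-5, power does rise, from about 59% to 72-88%. At a = 0.3, with both effects in the same direction, the unadjusted test is significant 93-98% of the time and the adjusted test 68-84%. No general power gain is claimed.

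**Conclusion.** The point holds in limited form. As written, the first regression cannot separate the two parts of Objective 3, and a marker of starting severity could be reported as a predictor of outcome. Over baseline-endpoint correlations of 0.3 to 0.7, the excess over the nominal 5% is nil if the marker is unrelated to baseline CAPS-5, and slight at correlation 0.1. It becomes material at about 0.2 to 0.3, where rejection is 8-45%. These sizes depend wholly on assumed correlations, on N = 76 with complete data, and on normality. The matter is minor: it concerns an exploratory process objective in a pilot, and no primary, secondary or safety conclusion depends on it.

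**What to change.** In Section 12.0:

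1. Reword the garbled sentence so that predictor, response and time points are clear.
2. Regress end-of-Stage-1 CAPS-5 on each baseline biomarker with baseline CAPS-5 as a covariate, and base any claim of predicting treatment outcome on that model only.
3. Report the association of each baseline biomarker with baseline CAPS-5 separately, as the answer on severity at baseline.
4. Label both results exploratory.

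Baseline CAPS-5 is already collected at Screen 2, so no new data are needed. The cost is one degree of freedom, one extra regression per marker, and fewer significant results for markers that also track baseline severity. This change does not by itself answer the part of Objective 3 about marijuana concentration, which needs treatment group in the model.
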